#### IV. Research Methods

### A. Outcome Measure(s):

The primary outcome measure will be extent of tumor resection. For all patients, pre-operative imaging and post-operative imaging will be used to analyze the extent of resection of the tumors. In intracranial lesions, the use of volumetric imaging tools will be used to calculate the extent of tumor resection. In spinal lesions, manual measurement will be used to determine the extent of resection.

Secondary outcome measures include the subjective utility of fluorescein per the operating surgeon, as well as positive predictive value, sensitivity and specificity for extent of tumor resection. Additional outcome measure(s) will vary depending on the neurosurgical tumor removed. Intraoperative videos and images will be collected from the surgical case. Images obtained will be correlated to tissue biopsy and will aid in the analysis of fluorescein

[name]: 18-0242 Page 2 Version: 07/03/2019

extravasation in pediatric neurosurgical tumors. All tissue samples collected will be taken for histopathological analysis.

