#### E. Potential Scientific Problems:

One possible limitation of this study is the single-institution nature of the project. Because Children's Hospital Colorado is a high-volume center, we are confident that we will be able to enroll the number of subjects needed for successful data analysis. Once this pilot project is complete, one of the future directions will be to conduct a multi-site study that can account for inter-institutional variance.

Another possible limitation is the absence of randomization to a control arm. We plan to use resection rates reported in the literature, as well as historical controls from our institution to compare to tumor resection rates during this pilot study.

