Given this, we propose a 3:1 ratio of historical controls to fluorescein treated patients to match tumor location and histology. 150 historical controls will be pulled from the last ten years of Children's Hospital patients and matched to the 50 fluorescein treated cases on lesion location and pathology. This 3:1 ratio will strengthen our ability to objectively assess for adverse events related to sodium fluorescein as well as our extent of tumor resection analysis. Importantly, historical controls undergo stereotactic-guided tumor resection in a similar fashion to patients undergoing fluorescein administrations as outlined in our protocol.

All patients who undergo sodium fluorescein-aided resection will also have neuropathological analysis. We will analyze correlation of fluorescein staining to histopathology. Tissue obtained during the time of surgery will be used to correlate fluorescein staining to histopathological diagnosis. This data will be used to calculate sensitivity and specificity of fluorescein staining for tumors. Pre- and post-operative imaging will be used to assess the degree of the extent of resection in intraparenchymal tumors. Data collected from post-operative follow-up will be used to assess for potential complications/adverse reactions associated with sodium fluorescein administration.

For data analysis, extent of tumor resection will be compared as a continuous value across groups using a parametric ANOVA. Further calculations, such as sensitivity, specificity and positive predictive value will be calculated by contingency tables. Additionally, since group membership is not random we will run an adjusted analysis predicting the likelihood of tumor resection as a continuous outcome adjusting for demographic and co-morbidity factors. Significance will be assigned at p < 0.05.

Furthermore, adverse reactions and population/demographic data will be characterized using relative risk and odds ratios. Overall survival and progression free survival analysis will be characterized using Kaplan-Meier curves and compared across groups using a log rank test.

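### In a non-randomised comparison, neither the unadjusted ANOVA nor the adjusted model of the primary outcome is named as decisive, so a confounded contrast can carry the conclusion

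*Combined protocol and SAP*

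**What the plan says.** Section IV.A names one primary outcome: "The primary outcome measure will be extent of tumor resection". Section IV.F gives two analyses of it. In the first, "extent of tumor resection will be compared as a continuous value across groups using a parametric ANOVA". The second is introduced as an addition: "Additionally, since group membership is not random we will run an adjusted analysis predicting the likelihood of tumor resection as a continuous outcome", with the adjustment set described only as "adjusting for demographic and co-morbidity factors". The rule that follows is general: "Significance will be assigned at p < 0.05".

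The power calculation in the same section (Table 3) uses a one-way ANOVA. The section also plans 150 controls from the last ten years at the same hospital, three for each of 50 treated patients, matched on lesion location and pathology.

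Section IV.E, on limitations, says: "We plan to use resection rates reported in the literature, as well as historical controls from our institution" will serve for comparison. It gives no test, benchmark or threshold for the literature rates.

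Nowhere do the documents name a primary analysis, rank the two analyses, or say what will be concluded if they disagree.

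**The concern.** The plan's reason for adjusting is that the groups were not formed at random. That reason applies to the headline comparison first of all, yet the adjusted model is the add-on and the study is sized on the unadjusted test. A reader who follows the text would take the ANOVA result as the main finding.

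Matching deals with location and pathology as far as it succeeds. It does not deal with anything else that differs between prospectively enrolled patients and controls operated on up to ten years earlier, calendar period being the plainest example. The ANOVA as described ignores the matching, so it neither gains precision from it nor corrects any imbalance left where matching is incomplete.

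With 200 patients the comparison is precise enough for a modest bias to cross the 0.05 line. At stake is whether a significant result reflects fluorescein or a difference between the groups.

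**Working it through.** **Inputs from the documents.** Difference 16 points (93.1 − 77.1), SD 25 points, alpha 0.05 (section IV.F); 50 treated and 150 controls (sections IV.C and IV.F). Covariate strength (R²), covariate shift and the correlation between tests are not in the documents. They are assumed below and shown over a range.

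**Step 1: the plan's own figure.** For two equal groups of n, the noncentrality is (16/25) × √(n/2). With the noncentral t, two-sided 0.05:

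- n = 32 (total 64): 2.56, power 71.2%
- n = 40 (total 80): 2.86, power 80.7%
- n = 53 (total 106): 3.29, power 90.4%

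These are the smallest totals that reach 70%, 80% and 90%, so Table 3 (64, 80, 106) is reproduced exactly. A one-sided test would need 46, 62 and 84 (normal approximation), which does not match. Table 3 is therefore a correct two-sided calculation for the unadjusted contrast; the arithmetic is not at fault.

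**Step 2: precision of the planned comparison.** Ignoring the matching, SE = 25 × √(1/50 + 1/150) = 4.08 points. Power for 16 points is Φ(16/4.08 − 1.96) = Φ(1.96) = 97.5%.

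**Step 3: what a bias does, with no true effect.** A covariate that explains a share R² of the outcome variance and is shifted by s SD in favour of the treated group biases the unadjusted difference by 25 × √R² × s. For R² = 0.3 and s = 0.3 this is 25 × 0.548 × 0.3 = 4.1 points, or 4.1/4.08 = 1.006 standard errors. The chance of p < 0.05 is Φ(1.006 − 1.96) + Φ(−1.006 − 1.96) = 17.0% + 0.2% = 17.2%.

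Simulation of both tests on the same 50 + 150 patients (8,000 runs per row) gives these false significance rates:

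| R² | Shift (SD) | Bias (points) | Unadjusted | Correctly adjusted | Either |
|---|---|---|---|---|---|
| 0.3 | 0 | 0 | 4.6% | 4.8% | 7.2% |
| 0.1 | 0.3 | 2.4 | 8.7% | 4.6% | 10.6% |
| 0.3 | 0.3 | 4.1 | 17.2% | 5.0% | 19.6% |
| 0.5 | 0.3 | 5.3 | 24.5% | 5.1% | 27.4% |
| 0.3 | 0.5 | 6.8 | 38.7% | 5.2% | 41.5% |

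**Step 4: choice between the two tests, no confounding.** With balanced covariates, the two statistics correlate at about √(1 − R²). A correlation of 0.9 corresponds to R² = 0.19, and 0.8 to R² = 0.36. The chance that at least one of two tests is significant, from 1,000,000 bivariate normal draws, is 7.1% at 0.9 and 7.8% at 0.8. This counts results in either direction; in the favourable direction alone it is 3.5% and 3.9%, against 2.5% for a single test.

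**The case against.** The strongest reply is that the plan has a primary analysis in all but name: the study is sized on a one-way ANOVA and the adjusted model is only additional. That is a fair reading, and under it the at-least-one-of-two error rate does not apply. It does not remove the problem, because the lead test is then the one that the plan's own remark about non-random groups calls into question.

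Second, the ANOVA is not run on arbitrary controls. They are matched on location and pathology, and the plan says that their stereotactic-guided surgery was similar. This stands, and it should reduce confounding. What remains is everything not matched on.

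Third, section IV.E calls the study a pilot, and no rule for success is defined. This limits the consequences. The plan still attaches a significance level to the comparison, and a reader will use it.

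Two stronger readings are tempting and are not supported. One is that literature rates give a third route to p < 0.05 on the primary outcome. They appear only among the limitations, without a test or benchmark, and the significance rule does not mention them. The adult 77.1% serves the sample size only. The other is that multiplicity is the main harm. The two tests share the same patients and are highly correlated, so the inflation is small.

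**Conclusion.** The point holds for the choice between the unadjusted ANOVA and the adjusted model. Neither is named as decisive, and the text leans towards the one more exposed to confounding. The main harm is confounding: about 17% false significance instead of 5% under a bias of about 4 points, with a range of about 9% to 39% over the assumed scenarios. Choice between the tests is secondary, at about 7% to 8%.

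These rates rest on assumed covariate strength and shift; the documents give neither and do not show that such a bias exists. The 5% for the adjusted model requires that the confounder is measured and correctly modelled. If it lies outside the demographic and co-morbidity factors, the adjusted result is biased too, so the covariate list matters as much as the label. The documents do not support a claim that the study's result will be wrong, only that the plan leaves the less protected analysis free to decide it.

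**What to change.** State in section IV.F that:

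- the single primary test is the adjusted comparison of extent of resection between treated patients and the matched institutional controls, two-sided 0.05;
- the model accounts for the matching factors (location and pathology), a covariate list fixed before analysis and drawn from the demographic and co-morbidity data already collected, and year of surgery;
- the unadjusted ANOVA is descriptive, and any disagreement with the primary result is reported;
- literature rates are quoted as context and not tested.

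Dropping the reference to likelihood for a continuous outcome is a wording matter only.

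The cost is protocol text, slightly more analysis work and fewer routes to a significant headline. One item needs thought: treated patients are enrolled prospectively and controls are historical, so year and group may overlap little. A year term then relies on the trend within the controls and costs precision. Suppose controls are spread evenly over ten years and enrolment over the next three (assumed). The mean gap is 5 + 1.5 = 6.5 years. The within-group variance of year is (150 × 100/12 + 50 × 9/12)/200 = 6.44, and the between-group variance is 0.25 × 0.75 × 6.5² = 7.92. The variance inflation is (6.44 + 7.92)/6.44 = 2.23, so the SE rises to 4.08 × √2.23 = 6.1 points and power for 16 points falls to Φ(16/6.1 − 1.96), about 75%. Enrolment over two to four years gives about 78% to 72%. All of this is before any precision gained from the other covariates. The plan should therefore fix the form of the year term in advance and report the model without it as a sensitivity analysis.

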#### **Exclusion Criteria:**

- Tumor in functionally eloquent cortex that precludes maximal surgical resection
- Severe renal dysfunction
- Preoperative serum creatinine level > than normal range and GFR < 30.

- Severe liver dysfunction
- History of asthma or pulmonary spasm
- Known allergy to sodium fluorescein or any other contrast dye
- Previous administration of sodium fluorescein within the last 72 hours
- Pregnant or nursing mother
- Other unspecified reasons that, in the opinion of the investigator, make the subject unsuitable for enrollment.
- Tumors with primary differential diagnosis not included in the inclusion groups

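### The adverse-event comparison sets screened fluorescein patients against historical controls with no stated screening, and no adjustment is stated, although extent of resection is adjusted

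*Combined protocol and SAP*

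**What the plan says.** Section IV.F (Data Analysis Plan) gives the control group a safety purpose: "This 3:1 ratio will strengthen our ability to objectively assess for adverse events related to sodium fluorescein". The 150 controls come from the hospital's patients of the last ten years and are "matched to the 50 fluorescein treated cases on lesion location and pathology". No other eligibility condition for controls is stated.

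For extent of resection, the section gives a reason for adjusting, "since group membership is not random", and responds with an "adjusted analysis predicting the likelihood of tumor resection as a continuous outcome adjusting for demographic and co-morbidity factors". For harms it says only that "adverse reactions and population/demographic data will be characterized using relative risk and odds ratios". It names no covariates or strata and does not say whether the estimate uses the matching.

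The exclusions in section IV.B apply to enrolled, and therefore treated, patients. They include "History of asthma or pulmonary spasm", known allergy to fluorescein or another contrast dye, severe renal or liver dysfunction, eloquent-cortex tumors that rule out maximal resection, and unsuitability in the investigator's judgement. Nothing in the document applies these criteria to the controls.

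**The concern.** The plan's reason for adjusting resection holds equally for harms. Followed as written, the harm comparison sets a screened group against one drawn on lesion location and pathology. Pathology does not balance asthma, allergy, or renal or liver disease. Location may capture part of the eloquent-cortex exclusion, but only if it is matched finely, and the plan does not say how finely.

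If the excluded conditions raise the risk of general peri-operative events (respiratory events, nausea or vomiting, rash, neurological deficit), unscreened controls will have more of them for reasons unrelated to fluorescein. The relative risk would then be too low. The stake is a reassuring estimate for a drug given to children, on an outcome for which the controls are said to allow an objective assessment.

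The eloquent-cortex exclusion also bears on resection. Controls with such tumors would tend to have less complete resections, and the covariates named for the resection model are demographic and co-morbidity factors, not surgical accessibility.

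**Working it through.** **Plan's own figures.** Table 3 (difference 16, SD 25, alpha 0.05) gives totals of 64, 80 and 106 for 70%, 80% and 90% power. An exact two-group calculation reproduces all three. They concern resection only. The documents give no event rate, sample size or power for harms.

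**Inputs**
- From section IV.F: 50 treated patients and 150 controls.
- Assumed, because the documents give neither: p, the share of controls with an excluded condition, and k, the ratio of their event risk *without fluorescein* to that of other controls.

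**Bias from screening one group.** Let r be the event risk of children without an excluded condition who receive no fluorescein.
- Control risk = r[(1 − p) + pk] = r[1 + p(k − 1)].
- Treated risk = true RR × r, since all treated children are screened.
- Observed RR = true RR × 1/[1 + p(k − 1)].

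| p | k = 2 | k = 3 | k = 4 |
|---|---|---|---|
| 5% | 1/1.05 = 0.95 | 1/1.10 = 0.91 | 1/1.15 = 0.87 |
| 10% | 1/1.10 = 0.91 | 1/1.20 = 0.83 | 1/1.30 = 0.77 |
| 15% | 1/1.15 = 0.87 | 1/1.30 = 0.77 | 1/1.45 = 0.69 |

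For example, at p = 10% and k = 3 a true relative risk of 1.2 would be observed as 1.2/1.20 = 1.0.

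**Random error for comparison.** With true RR = 1 and event rate e (assumed), SE(log RR) = √[(1 − e)/(50e) + (1 − e)/(150e)].
- e = 10%: √(0.18 + 0.06) = 0.490. The 95% interval is exp(±0.960) = 0.38 to 2.61.
- e = 20%: √(0.080 + 0.027) = 0.327. The 95% interval is exp(±0.640) = 0.53 to 1.90.

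Every factor in the table lies inside both intervals.

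**A bias in the other direction.** Section IV.G.1.e has adverse events recorded prospectively at each visit in treated children. No such procedure is given for controls. If control charts capture a share s of events (assumed 70-90%), the RR is multiplied by 1/s, which is 1.43 to 1.11. At p = 10%, k = 2 and s = 90% the net factor is 1/(1.10 × 0.90) = 1.01, so the two effects cancel. At p = 10%, k = 2 and s = 80% it is 1/(1.10 × 0.80) = 1.14, so the direction reverses.

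**The case against.** **Controls cannot have dye reactions.** The hypersensitivity and respiratory reactions listed under Potential Risks (section IV.D) are reactions to fluorescein. A reader might infer that children prone to them inflate the control event rate. They do not, because controls receive no fluorescein. Screening for asthma and dye allergy lowers the treated group's dye-reaction risk and limits generalisability, but it does not raise the controls' rate of those reactions. This stands. The bias can act only through general peri-operative events, and k must be read on that scale. Such events do enter the comparison in principle, since section IV.G counts events whether or not they are drug related. Section IV.G.1.f, however, takes a list of common surgical events out of standard reporting, so which events will be compared is itself unsettled.

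**The argument rests on silence.** A reader might infer that the controls are a sicker population. The documents do not say so. They say only that controls are matched on two factors and were operated on in a similar way. Equally, they do not say that the relative risk ignores the matching. What stands is that control eligibility and the form of the estimate are unspecified.

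**The net direction is not known.** A reader might infer that the reported comparison must favor fluorescein. Under-recording in control charts would push the other way. Section IV.F does claim reliable follow-up of historical patients for neurologic reactions, but it sets out no collection method. One bias does not excuse the other, yet neither alone fixes the sign of the result.

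**Little turns on it.** The move to the second phase rests on the safety committee's review of events (section IV.H), and no stopping criterion refers to a relative risk against controls. This limits the weight of the point. It does not remove it, because the plan presents the control comparison as evidence on harm.

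**Conclusion.** The point holds as a gap in specification. The plan recognises non-random membership, acts on it for resection, and states no action for harms. It screens the treated group without stating a corresponding screen for controls. For general peri-operative events, and taken alone, this would tend to make fluorescein look safer.

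The size is not derivable from the documents. The factor of 0.95 to 0.69 rests wholly on the assumed 5-15% prevalence and 2-4 times the risk, and it shrinks towards 1 if the excluded conditions have little effect on events without fluorescein. It is smaller than the sampling error at 50 against 150 and could be offset by unequal recording. The change is worth making before controls are drawn, because a restriction chosen afterwards would be post hoc. It does not by itself undermine the study.

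**What to change.** 1. **Control draw.** State that every section IV.B exclusion that charts can show applies to controls, for both the harm and the resection comparisons: asthma or pulmonary spasm, contrast allergy, severe renal or liver dysfunction, and eloquent-cortex tumor. Investigator discretion cannot be reproduced from charts and should be named as a remaining difference.
2. **Estimate.** Report the adverse-event relative risk stratified by matched set (Mantel-Haenszel) with a confidence interval. This step does not remove the screening bias. With complete 1:3 sets, A treated events and B control events, the stratified estimate is (A × 3/4)/(B × 1/4) = 3A/B, and the unstratified one is (A/50)/(B/150) = 3A/B. The restriction in step 1 does the correcting. Stratifying makes the interval respect the matching and handles incomplete sets.
3. **Covariates.** Add age or co-morbidity only as a sensitivity analysis where event counts allow. At a 10% event rate (assumed) there would be about 5 treated and 15 control events, too few for a full model.
4. **Fluorescein-attributed events.** Report these descriptively in the treated group, since controls cannot have them.

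**Cost.** A chart filter, much of it on co-morbidity data the resection model already needs, and a few sentences in section IV.F. The downside is a somewhat smaller control pool and a slightly wider interval.

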#### Schedule of Events:

Table 1: Schedule of Events	Preop Assessment		ery and patient Stay	Outpatient Follow-Up
Visit Type (Standard of Care)	Neurosurgery Visit/Consult/H&P	Day of Surgery	Prior to Discharge	 Follow-Up Visit(s) Discharge through Month 2
Informed Consent/Assent	X			
Eligibility Assessment	X			
△Demographics	X			
△Medical History	X			
△Neurologic Exam	X		X	X
△Medical Exam	X		X	X
△Imaging (MRI/CT) of the brain and/or Spine	Х		Х	X
Δ Serum Creatinine	X			
△Pregnancy Test	X			
Sodium Fluorescein Administration		Х		

[name]: 18-0242 Page 4 Version: 07/03/2019

△Tumor Resection Surgery	X		
△Intraoperative	X		
Photography/Videography			
△Tumor Biopsy/Pathology	X		
Adverse Events	X	X	Χ

<sup>ΔStandard of care procedures, data will be collected via chart review.

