[name]: 18-0242 Page 6 Version: 07/03/2019

physical, neurologic exam data, and may also include laboratory findings and post-operative imaging studies. These will all be documented clinically and recorded via chart review for the study. Patients will be followed for the study through Month 2 (or 8 weeks) post-surgery.

Furthermore, any adverse events occurring after surgery will be collected until 7 (for non-serious AEs) or 30 days (for SAEs) after the last day of study intervention (administration of fluorescein). All adverse events will be followed for outcome information until resolution or through Month 6 post-surgery.

For example, if a patient has no adverse events following surgery, they will only be followed through end of study period which is 2 months post-surgery. If the patient had adverse events within the first 30 days, those adverse events will be followed through resolution or 6 months post procedure, whichever comes first.

Re-Enrollment: Patients who have previously been enrolled in this study and received prior administration of fluorescein sodium as a part of this study for guided tumor resection are eligible for re-enrollment into the study, should further surgical resection be clinically indicated. Patients will receive the same dosage as outlined in the protocol of 3mg/kg. Clearance of 500mg of fluorescein sodium is 24-72 hours after administration of a single dose [16]. Patients re-enrolled into the study will be eligible after 3 days given the clearance time necessary for fluorescein sodium. Patients will be enrolled with the same study number. Patients will be reconsented at time of re-enrollment.

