## e. Time Period and Frequency for Event Assessment and Follow Up

21 CFR 312.64(b) requires that the Site Principal Investigator records non-serious adverse events and reports them to the Sponsor according to the timetable for reporting specified in the protocol.

A properly delegated study team member will record all adverse events with start dates occurring any time after administration of fluorescein until 7 (for non-serious AEs) or 30 days (for SAEs) after the last day of study intervention. All events will be followed for outcome information until resolution or stabilization or through Month 6 post-surgery.

All AEs occurring while on study will be documented regardless of their relationship to the study intervention, and whether or not they meet the definition of an SAE. AEs will be captured, reviewed and assessed by an LIP member of the study team. The outcome of this review and assessment will be documented by a properly delegated study team member on an Adverse Event Log. Information to be collected includes event description, time of onset (start date) and time of resolution/stabilization of the event (end date), and the LIP's assessment of expectedness, severity and relationship to study intervention.

Any medical condition that is present at the time the participant is screened will be considered as baseline medical history, and will not be recorded as an AE. However, if the study participant's condition deteriorates at any time during the study, the event will be recorded as an AE.

Changes in the severity or frequency of an AE will be documented as separate events to allow an assessment of the duration of the event at each level of severity or frequency.

AEs characterized as intermittent will be documented with onset and duration of each episode.

At each study visit, a properly delegated study team member will document all occurrences of AEs and SAEs since the last visit. This information will be gathered through direct observation (e.g. rash), elicited from or spontaneously volunteered by the participant, documentation in Medical Records, laboratory or other clinical reports or notes, or identified in patient-reported outcome tools (e.g. diaries, surveys, questionnaires), or any other means.

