## f. Adverse Event Reporting

Adverse Event Reporting will be performed in accordance with the study protocol, any contractual agreement, and all IRB requirements.

21 CFR 312.64(b) requires that the Site Principal Investigator records non-serious adverse events and reports them to the Sponsor according to the timetable for reporting specified below.

**Disease-Related Events (DREs):** The following disease-related events (DREs) are expected and common with brain tumor surgery, and will not be reported per the standard process for adverse event reporting: bleeding in the brain, injury or swelling to the brain, infection in the brain or at wound site, meningitis, seizures, hydrocephalus, cerebral spinal fluid leakage, the need for

[name]: 18-0242 Page 11 Version: 07/03/2019

additional surgery, tearing of the eyes, damage to the eye, blood clots, stroke, dizzy spells, recurrence or tumor growth, postoperative pain and allergic reactions to anesthesia.

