# g. Serious Adverse Event Reporting

The Site Principal Investigator will immediately report to the Sponsor any serious adverse event, whether or not considered study intervention related, including those listed in the protocol or investigator brochure, and will include the study team LIP's assessment of whether there is a reasonable possibility that the study intervention caused the event.

Study endpoints that are serious adverse events (e.g. all-cause mortality) will be reported in accordance with the protocol unless there is evidence suggesting a causal relationship between

[name]: 18-0242 Page 12 Version: 07/03/2019

the study intervention and the event (e.g., death from anaphylaxis). In that case, the Site Principal Investigator must immediately report the event to the Sponsor.

All SAEs will be followed until satisfactory resolution or until the study team's LIP deems the event to be chronic or the participant is stable.

Serious adverse events that are considered related (i.e., determined to be possibly, probably, or definitely related) to the investigational product by the Sponsor will be followed until the event resolves or stabilizes. Any SAE that occurs after treatment completion, and is considered by the Sponsor to be related to the investigational product, will be documented and reported as appropriate.

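### Overall and progression-free survival are to be compared by log-rank test, but study follow-up of treated patients ends at Month 2, so the test can address only about the first 8 weeks

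*Combined protocol and SAP*

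**What the plan says.** Section IV.F commits to a between-group survival comparison: "Overall survival and progression free survival analysis will be characterized using Kaplan-Meier curves and compared across groups using a log rank test". The groups are 50 fluorescein-treated patients and matched historical controls: "150 historical controls will be pulled from the last ten years". The same section sets significance at p < 0.05.

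The Follow-Up paragraph of section IV.C fixes how long treated patients are observed: "Patients will be followed for the study through Month 2 (or 8 weeks) post-surgery". It then confirms that a patient without adverse events is followed no further than that. The last column of the Schedule of Events (Table 1) agrees: "Follow-Up Visit(s) Discharge through Month 2". On what is assessed after surgery, the Follow-Up paragraph says that the evaluation "may also include laboratory findings and post-operative imaging studies".

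Longer follow-up appears only for adverse events. Section IV.G.1.e says: "All events will be followed for outcome information until resolution or stabilization or through Month 6 post-surgery". Section IV.G.1.g says: "All SAEs will be followed until satisfactory resolution", or until the event is judged chronic or the participant stable. It also provides for documenting later SAEs that the sponsor considers related to the product. New events are otherwise recorded for 7 days (non-serious) or 30 days (serious) after fluorescein. Section IV.G.1.f lists, among the disease-related events left out of the standard reporting process, "recurrence or tumor growth, postoperative pain and allergic reactions to anesthesia".

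Section IV.A does not name overall survival (OS) or progression-free survival (PFS), though it leaves room for further outcomes that depend on tumor type. No section gives a PFS definition, a time origin, a survival horizon or a censoring rule for either group.

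**The concern.** The analysis and the data collection do not fit together. OS and PFS are normally read over months or years, but the treated patients' study data stop at 8 weeks. Controls drawn from ten years of records may have far longer follow-up, although the plan does not say how much will be used.

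Three things are at stake:

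- A non-significant log-rank result could be read as evidence of no survival difference when the test had little chance of finding one. This matters because section IV.I names better overall survival as a potential gain from the technique.
- If the control curves run past Month 2, the Kaplan-Meier plot will show a stretch with no treated patients beside it.
- PFS is weaker still, because post-operative imaging within the 8 weeks is possible but not assured.

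**Working it through.** **1. The plan's own sample-size figure.** Table 3 gives total N of 64, 80 and 106 for 70%, 80% and 90% power. A two-group ANOVA (equivalently a two-sided t-test) with difference 16, SD 25 and alpha 0.05, rounded up per arm, reproduces all three exactly. They concern extent of resection only. No event count, hazard ratio or horizon is given for OS or PFS.

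**2. Why control follow-up does not help.** At each event time, the log-rank score adds (observed treated events) − (treated at risk ÷ all at risk). Its variance adds p(1 − p), where p is the treated share at risk. Once every treated patient is censored, p = 0 and both terms are zero. As a check, one simulated dataset with controls followed for 8, 52 or 520 weeks had 8, 42 or 147 events in total, yet the same score (−1.000) and the same variance (1.500) each time.

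**3. Events expected by 8 weeks.** From the documents: 50 treated, 150 controls (treated share 0.25), alpha 0.05, taken as two-sided. Assumed, because the documents give neither: control event risk r by 8 weeks, and hazard ratio HR.

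Events d = 150r + 50[1 − (1 − r)^HR]. For r = 5% and HR 0.5: 7.5 + 50(1 − 0.95^0.5) = 7.5 + 1.27 = 8.8.

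Schoenfeld power = Φ(√(d × 0.25 × 0.75) × |ln HR| − 1.960). For d = 8.8 and HR 0.5: Φ(0.889 − 1.960) = 14.2%.

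| Control risk by 8 weeks | Events, HR 0.5 | Formula power, HR 0.5 | Simulated power, HR 0.5 | Events, HR 0.7 | Formula power, HR 0.7 |
|---|---|---|---|---|---|
| 2% | 3.5 | 8.1% | 0.8% | 3.7 | 4.8% |
| 5% | 8.8 | 14.2% | 2.8% | 9.3 | 6.8% |
| 10% | 17.6 | 24.1% | 13.1% | 18.6 | 9.8% |
| 20.6% (6-month control median) | 36 | 44% | 30% | 38 | 16% |

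The simulation used 4,000 runs per row, exponential times and censoring of everyone at 8 weeks. It falls below the formula because the normal approximation is optimistic with so few events.

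**4. Events needed for 80% power.** (1.960 + 0.842)² ÷ (0.25 × 0.75 × (ln HR)²):

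- HR 0.5: 7.849 ÷ (0.1875 × 0.4805) = 87.1, so 88 events.
- HR 0.7: 7.849 ÷ (0.1875 × 0.1272) = 329.05, so 330 events, more than the 200 patients.

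**5. Best case for the treated group.** Suppose no treated patient has an event and D controls do. The treated share at the successive events is 50/(200 − i), for i = 0 to D − 1.

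- D = 11: chi-square 3.79, p = 0.051.
- D = 12: chi-square 4.15, p = 0.042.

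So even a perfect treated group needs at least 12 control events within 8 weeks. Risks of 2%, 5% and 10% give 3, 7.5 and 15.

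**The case against.** The strongest reply is that treated patients are followed by standard care and chart review, so later survival data would exist in the records, and the 8-week limit binds only if the analysis is confined to the study follow-up. That is true of the records but not of the plan: the Follow-Up paragraph bounds data collection for the study at Month 2. Using later charts is a sound remedy, but it has to be written down, with a common horizon.

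The Month 6 and SAE follow-up might seem to fill the gap. It tracks the outcomes of adverse events, so using it for survival would make the length of observation depend on having had an event. The exclusion of recurrence from adverse-event reporting does not show that progression goes unrecorded, since charts and imaging could show it. It shows only that the adverse-event system is no substitute for progression follow-up.

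It is also fair to say that OS and PFS are not named outcomes, carry no power claim and take one sentence in what section IV.E calls a pilot project, and that section IV.I speaks only of potential. This limits the weight of the point but does not remove the conflict.

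On size, every event rate is assumed, and at the highest risk considered power is well above that at 2% to 10%, though still low. The 330-event figure for HR 0.7 is a limit of sample size that longer follow-up would not cure. The missing PFS definition, time origin and censoring rule are separate gaps and do not follow from the Month 2 limit.

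**Conclusion.** The concern holds. Sections IV.C and IV.F conflict: as written, the OS and PFS log-rank tests are confined to about 8 weeks. That conclusion rests on the text and on how the test works, not on any assumed rate.

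The size does rest on assumptions: 8-week control risk of 2% to 20.6%, hazard ratios of 0.5 and 0.7, and exponential times. Across that range formula power is 5% to 44%, and simulated power at a hazard ratio of 0.5 is about 1% to 30%. None of these reaches 80%. The primary analysis of extent of resection is not touched. The plan should be corrected, and the correction is cheap.

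**What to change.** Choose one of two changes.

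**(a) Drop the test.** Delete the OS and PFS log-rank comparison from section IV.F. Report 8-week mortality, and progression where post-operative imaging exists, descriptively with exact 95% intervals and with controls truncated at 8 weeks. This costs only wording and gives up a test that could show little.

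**(b) Collect the data.** Amend the Follow-Up paragraph so that vital status and progression are taken from routine charts to one stated horizon in both groups. Measure time from surgery, define PFS, and censor both groups at that horizon. Stratifying the log-rank test by the tumor type already used for matching is a modest gain in efficiency, not a necessity. State that the comparison is supplementary and that power may still be low. This needs an amendment and longer chart review, but no added visits. Whether the consent wording would have to change cannot be judged here, because the consent pages were removed before review.
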